11.7 Toxicity Stopping Rule

After 20 patients have been accrued to each arm and treated for at least two cycles of therapy the rate of unacceptable toxicity will be determined in each arm and compared between arms. Unacceptable toxicities in this context are defined as any Grade 3 or higher non-hematologic toxicity or any Grade 4 or higher hematologic toxicity. If the proportion of patients experiencing an unacceptable toxicity is significantly higher in Arm 2 (the arm with the larger carfilzomib dose) than in Arm 1 (the arm with the lower carfilzomib dose) a recommendation will be made to close the study to further accrual. With 20 patients per arm there is at least 83% power to detect a difference of 40% between arms. These calculations are based on the assumption that the number of patients experiencing an unacceptable toxicity as defined above are binomially

distributed and a one-sided significance test of 0.1. The DSMC will be responsible for decisions regarding possible termination and/or early reporting of the study, and any major study amendments.

11.8 Toxicity Monitoring

All eligible patients that have initiated treatment will be considered evaluable for toxicity analyses. The maximum grade for each toxicity will be recorded for each patient, and frequency tables will be reviewed to determine toxicity patterns. With 72 patients per study arm, the probability of any particular toxicity can be estimated within $\pm 14\%$ (95% confidence interval). Any toxicity having a true occurrence rate of 5% or more within one of the treatment arms is very likely to be observed in at least one patient (probability $\geq 96\%$).

A Data and Safety Monitoring Committee will oversee the conduct of the study. The Committee consists of four members from outside of the SWOG, 3 SWOG members, 3 non-voting representatives from the National Cancer Institute (NCI), and the Group Statistician (non-voting). The members of this Committee will receive confidential reports every 6 months from the SWOG Statistical Center, and will meet at the Group's bi-annual meetings as necessary. They will receive additional reports, if needed, for assessment of adverse events, or other study related matters. The Committee will be responsible for decisions regarding possible termination and/or early reporting of the study.

In addition to the above DSMC review, toxicity and accrual monitoring during the randomized Phase II portion will be done routinely by the Study Chair, Study Statistician and the Disease Committee Chair. Endpoint monitoring is done by the Study Statistician and Study Chair. Accrual reports are generated weekly and formal toxicity reports are generated every 6 months. In addition, the Statistical Center, Serious Adverse Event Coordinator at the Operations Office, SAE Physician Reviewer and Study Chair monitor toxicities on an ongoing basis.

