The purpose of this memorandum is to clarify an error noted in protocol Section 11.8 Toxicity Monitoring. The first paragraph of Section 11.8 (excerpted below for ease of reference) currently indicates, "With 72 patients per treatment arm." This statement is incorrect and will be modified in the next revision to the protocol to read "With **63** patients per treatment arm," as is congruent with the protocol design.

"All eligible patients that have initiated treatment will be considered evaluable for toxicity analyses. The maximum grade for each toxicity will be recorded for each patient, and frequency tables will be reviewed to determine toxicity patterns. With **72** patients per study arm, the probability of any particular toxicity can be

estimated within $\pm 14\%$ (95% confidence interval). Any toxicity having a true occurrence rate of 5% or more within one of the treatment arms is very likely to be observed in at least one patient (probability $\geq 96\%$)."

This memorandum serves to notify the NCI, Alliance, ECOG-ACRIN, and the SWOG Statistical Center.

cc: PROTOCOL AND INFORMATION OFFICE
[name] – Alliance
[name] – ECOG-ACRIN
[name] – ECOG-ACRIN
[name] – Biologics
[name] – Amgen

June 1, 2016

TO: ALL NATIONAL CLINICAL TRIALS NETWORK MEMBERS; CTSU
FROM: [name], MIIM, Protocol Coordinator (E-mail: [contact])
RE: **S1304**, "A Phase II Randomized Study Comparing Two Doses of Carfilzomib (NSC-756640) with Dexamethasone for Multiple Myeloma Patients with Relapsed or Refractory Disease". Study Chairs: Drs. [name], [name], [name], [name] and [name].

GROUP CHAIR'S OFFICE

[name]
CHAIR

[name]

[name]
[name]

[contact]

[contact] FAX

OPERATIONS OFFICE

[name]
[name]
[name]
[contact]
[contact] FAX

STATISTICAL CENTER

[name]
[name]
[name]
[contact]
[contact] FAX

[name]
[name]
[name]
[name]
[contact]
[contact] FAX

swog.org

MEMORANDUM

Study Chair: [name]
[contact]
E-mail: [contact]

IRB Review Requirements

() Full board review required
() Expedited review allowed
(√) No review required

Status Change

() IRB Review only
() Activation
() Closure: Permanent
() Reactivation

Protocol changes

() Eligibility changes
() Treatment / Dose Modification / Study Calendar changes
() Informed Consent changes
() Patient notification not required

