11.2 Sample Size and Power Justification

Sixty-three eligible patients will be accrued to each treatment arm unless undue toxicity is encountered. The study anticipates an accrual of 72 eligible patients per year, based on recent ECOG accrual estimates for intergroup trials in this patient population. Thus 126 patients will be accrued in approximately 1.75 years. The study anticipates accruing an additional 14 patients to account for ineligibilities and withdrawal of consent for a total of 140 patients.

A median PFS of 9 months is anticipated in Arm 1, based on previous trials using this treatment combination in this patient group (Onyx, personal conversations). With 1.75 years of patient accrual and 1.5 years of follow-up 63 patients per arm results in a study with 90% power to detect a hazard ratio of 1.67, which corresponds to an increase in median PFS from 9 months to 15 months in Arm 2, the arm with the higher carfilzomib dose. These calculations are based on a one-sided stratified log rank test at level (alpha) of 0.1 and on the assumption that progressions are exponentially distributed.

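### Section 11.8 states ±14% precision for a toxicity rate, but 63 patients per arm give about ±12% to ±13%; the memorandum correcting 72 to 63 leaves the 14% (minor, conservative)

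*Combined protocol and SAP*

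**What the plan says.** Section 11.8 (Toxicity Monitoring) says that with 72 patients in each arm "the probability of any particular toxicity can be estimated within" ±14%, described as a 95% confidence interval. It adds that a toxicity with a true rate of 5% or more in an arm "is very likely to be observed in at least one patient", with probability of at least 96%. It names no interval method and no assumed toxicity rate. The analysis set is defined there too: "All eligible patients that have initiated treatment will be considered evaluable for toxicity analyses".

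Section 11.2 sets the design size: "Sixty-three eligible patients will be accrued to each treatment arm unless undue toxicity is encountered".

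The memorandum on Section 11.8, at the front of the document, acknowledges the 72. It says "This statement is incorrect and will be modified in the next revision to the protocol to read" 63 per arm, "as is congruent with the protocol design". It reprints the excerpt with the 14% and the 96% and announces no change to either. The 72 is therefore already dealt with. The point here is the 14% that stays beside the corrected number.

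**The concern.** A confidence half-width for a proportion follows from the sample size, the confidence level and the assumed rate. If the sample size in the sentence is corrected, the half-width should be checked against it. Here the 14% matches neither the printed 72 nor the corrected 63, while the 96% in the next sentence matches 63. Making the correction as announced would reissue the paragraph with one figure that does not follow from its stated sample size.

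What is at stake is limited. Safety is a secondary objective (Section 1.2c), and this is the protocol's general statement of how precisely a toxicity rate will be known in each arm. A reader who relies on it would expect slightly less precision than the design gives.

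**Working it through.** **Inputs.** n = 63 per arm (Section 11.2 and the memorandum); n = 72 per arm (Section 11.8 as printed); two-sided 95% confidence; stated half-width 14%; stated probability of at least 96% for a 5% toxicity (all Section 11.8). The true toxicity rate is not given. I assume p = 0.5, which makes the interval widest, because the sentence covers any toxicity.

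**Step 1: try to reproduce ±14%.** The formulas at p = 0.5 are:

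- Wald: 1.96 × 0.5 / √n. At 63: 0.98 / 7.937 = 0.1235. At 72: 0.98 / 8.485 = 0.1155.
- Continuity-corrected Wald: add 1/(2n). At 63: 0.1235 + 0.0079 = 0.1314. At 72: 0.1155 + 0.0069 = 0.1224.
- Wilson: 1.96 × 0.5 / √(n + 1.96²). At 63: 0.1199. At 72: 0.1125.
- Clopper-Pearson: limits from beta quantiles, maximised over all possible counts. I give both half the interval length and the larger of the two distances from estimate to limit.

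| Method (95%, worst case) | n = 63 | n = 72 | n at which the width is 14% |
|---|---|---|---|
| Wald | 12.3% | 11.5% | 49 |
| Continuity-corrected Wald | 13.1% | 12.2% | 56 |
| Wilson | 12.0% | 11.3% | about 45 |
| Clopper-Pearson half-width | 12.9% | 12.0% | 53 to 54 |
| Clopper-Pearson larger side | 13.1% | 12.2% | 56 |

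The last column for Wald is (1.96 × 0.5 / 0.14)² = 49.0. For Wilson it is 49.0 − 3.84 = 45.2. The Clopper-Pearson half-width is 14.05% at 53 and 13.92% at 54. At 56 the larger-side distance is 13.96% and the continuity-corrected width 13.99%.

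The 14% is not reproduced: no method gives a value that rounds to 14% at 63 or at 72. Another confidence level does not explain it either. At n = 63 the Wald half-width is 10.4% at 90% confidence and 16.2% at 99%.

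**Step 2: check the companion figure.** The probability of at least one event at a 5% rate is 1 − 0.95ⁿ.

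- n = 63: 0.9605
- n = 72: 0.9751
- n = 56: 0.9434
- n = 49: 0.9190

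The smallest n that reaches 96% is ln(0.04) / ln(0.95) = 62.75, so 63. The 96% figure is correct for the design size.

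**Step 3: compare.** The sample sizes that would make 14% the calculated width give less than 96% in the next sentence. The two figures in the paragraph therefore do not come from one common n.

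**Step 4: size.** At n = 63 the stated width exceeds the calculated one by 14.0 − 12.3 = 1.7 points (Wald), 14.0 − 12.9 = 1.1 (Clopper-Pearson half-width) or 14.0 − 13.1 = 0.9 (larger side). With Wilson the gap is 14.0 − 12.0 = 2.0.

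**The case against.** The strongest reply is that the sentence is not false. A rate estimated to within 14 points is also a true description when the widest method gives 13.1. This stands. The figure errs on the safe side and holds as an upper bound at both 63 and 72.

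A second reply is that 14% could be 13.1% (larger-side exact or continuity-corrected, n = 63) rounded up to the next whole percent. That is arithmetically possible, and no interval method is named to rule it out. Nothing in the text supports it, though, and at the printed 72 the widest method, 12.2%, would round up only to 13%.

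A third reply is that the evaluable set may be smaller than 63, since it counts only eligible patients who began treatment, and the closure memorandum mentions more ineligibility than anticipated. The documents give no evaluable count and no allowance for a smaller one, and the 96% in the same paragraph needs at least 63. This does not rescue the 14%, but it is a reason to state the n that the replacement figure assumes.

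Finally, the memorandum set out to correct only the 72, and accrual is permanently closed. Both are true. They limit the consequence without making the number right.

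**Conclusion.** The 14% does not follow from 63 or from 72 patients per arm. At the design size the worst-case 95% half-width is about 12% to 13%, so the stated width is too large by roughly 1 to 2 points. This rests on p = 0.5, a two-sided 95% interval and 63 evaluable patients per arm. Lower or higher toxicity rates would narrow the interval further under the Wald formula.

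Severity is minor. A reader might infer three stronger things, none of which the documents support:

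- **That the trial claims more precision than it has.** The reverse holds: the stated width is larger than the calculated one.
- **That safety decisions rest on a wrong number.** The ±14% enters no sample size, test or boundary. The stopping rule in Section 11.7 has its own calculation at 20 patients per arm, and the cardiovascular comparison in Section 11.6 has its own power statement. Reported intervals will come from observed counts.
- **That the gap equals a fixed loss of patients.** It is 63 − 49 = 14 under Wald, but 9 to 10 for the Clopper-Pearson half-width and 7 for the larger-side or continuity-corrected width. No single equivalent should be quoted.

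**What to change.** In the revision that changes 72 to 63 in Section 11.8, also replace ±14% with one of the following, and name the method:

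- approximately ±13% (worst case, Clopper-Pearson half-width 12.9%), or
- ±12% (worst case, Wald 12.3%).

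The word approximately matters in the first option, because the exact larger-side distance is 13.1% and slightly exceeds a strict 13% bound. If the sponsor prefers to keep 14% as a rounded-up bound, the sentence should say so and name the method. Leave the statement of at least 96% as it is. The cost is one number and a few words in a sentence already due for revision. Nothing in the design, conduct or analysis changes.

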12.0 DISCIPLINE REVIEW

This study will not utilize discipline review.

13.0 REGISTRATION GUIDELINES

13.1 Registration Timing

Patients must be registered prior to initiation of treatment (no more than five working days prior to planned start of treatment).

13.2 Investigator/Site Registration

Prior to the recruitment of a patient for this study, investigators must be registered members of a Cooperative Group. Each investigator must have an NCI investigator number and must maintain an "active" investigator registration status through the annual submission of a complete investigator registration packet to CTEP.

a. CTEP Investigator Registration Procedures

Food and Drug Administration (FDA) regulations and National Cancer Institute (NCI) policy require all investigators participating in any NCI-sponsored clinical trial to register and to renew their registration annually.

Registration requires the submission of:

- a completed **Statement of Investigator Form** (FDA Form 1572) with an original signature
- a current Curriculum Vitae (CV)
- a completed and signed **Supplemental Investigator Data Form** (IDF)
- a completed **Financial Disclosure Form** (FDF) with an original signature

Fillable PDF forms and additional information can be found on the CTEP website at <http://ctep.cancer.gov/investigatorResources/investigator_registration.htm>.

For questions, please contact the **CTEP Investigator Registration Help Desk** by email at <[contact]>.

b. CTEP Associate Registration Procedures

The Cancer Therapy Evaluation Program (CTEP) Identity and Access Management (IAM) application is a web-based application intended for use by both Investigators (i.e., all physicians involved in the conduct of NCI-sponsored clinical trials) and Associates (i.e., all staff involved in the conduct of NCI-sponsored clinical trials).

Associates will use the CTEP-IAM application to register (both initial registration and annual re-registration) with CTEP and to obtain a user account.

Investigators will use the CTEP-IAM application to obtain a user account only. (See CTEP Investigator Registration Procedures above for information on registering with CTEP as an Investigator, which must be completed before a CTEP-IAM account can be requested.).

An active CTEP-IAM user account will be needed to access all CTEP and CTSU (Cancer Trials Support Unit) websites and applications, including the CTSU members' website.

Additional information can be found on the CTEP website at http://ctep.cancer.gov/branches/pmb/associate_registration.htm. For questions, please contact the **CTEP Associate Registration Help Desk** by email at [contact].

c. CTSU Registration Procedures

Each investigator or group of investigators at a clinical site must obtain IRB approval for this protocol and submit IRB approval and supporting documentation to the CTSU Regulatory Office before they can be approved to enroll patients. Study centers can check the status of their registration packets by querying the Regulatory Support System (RSS) site registration status page of the CTSU members' website by entering credentials at <https://www.ctsu.org>. For sites

1. Downloading Site Registration Documents:

Site registration forms may be downloaded from the **S1304** protocol page located on the CTSU members' website.

- Go to <https://www.ctsu.org> and log in to the members' area using your CTEP-IAM username and password
- Click on the Protocols tab in the upper left of your screen
- Click on the SWOG link to expand, then select **S1304**. Click on the Site Registration Documents link.

2. Requirements for S1304 Site Registration:

- CTSU IRB Certification (for sites not participating via the NCI CIRB)
- CTSU IRB/Regulatory Approval Transmittal Sheet (for sites not participating via the NCI CIRB)

3. Submitting Regulatory Documents:

Submit completed forms along with a copy of your IRB Approval and Model Informed Consent to the CTSU Regulatory Office, where they will be entered and tracked in the CTSU RSS.

CTSU Regulatory Office
[name]
[name]
[contact]
[contact]
E-mail: [contact] (for regulatory document submission only)

4. Checking Your Site's Registration Status:

Check the status of your site's registration packets by querying the RSS site registration status page of the members' section of the CTSU website. (Note: Sites will not receive formal notification of regulatory approval from the CTSU Regulatory Office.)

- Go to <https://www.ctsu.org> and log in to the members' area using your CTEP-IAM username and password
- Click on the Regulatory tab at the top of your screen
- Click on the Site Registration tab
- Enter your 5-character CTEP Institution Code and click on Go

13.3 OPEN Registration Requirements

The individual registering the patient must have completed the appropriate SWOG Registration Worksheet. The completed form must be referred to during the registration but should not be submitted as part of the patient data.

Patient enrollment will be facilitated using the Oncology Patient Enrollment Network (OPEN). OPEN is a web-based registration system available on a 24/7 basis. To access OPEN, the site user must have an active CTEP-IAM account (check at <<https://eapps-ctep.nci.nih.gov/iam/index.jsp>>) and a 'Registrar' role on either the LPO or participating organization roster.

OPEN will also ask additional questions that are not present on the SWOG Registration Worksheet. The individual registering the patient must be prepared to provide answers to the following questions:

- a. Institution CTEP ID
- b. Protocol Number
- c. Registration Step
- d. Treating Investigator
- e. Credit Investigator
- f. Patient Initials
- g. Patient's Date of Birth
- h. Patient SSN (SSN is desired, but optional. Do not enter invalid numbers.)
- i. Country of Residence

- j. ZIP Code
- k. Gender (select one):
 - Female Gender
 - Male Gender
- l. Ethnicity (select one):
 - Hispanic or Latino
 - Not Hispanic or Latino
 - Unknown
- m. Method of Payment (select one):
 - Private Insurance
 - Medicare
 - Medicare and Private Insurance
 - Medicaid
 - Medicaid and Medicare
 - Military or Veterans Sponsored NOS
 - Military Sponsored (Including Champus & Tricare)
 - Veterans Sponsored
 - Self Pay (No Insurance)
 - No Means of Payment (No Insurance)
 - Other
 - Unknown
- n. Race (select all that apply):
 - American Indian or Alaska Native
 - Asian
 - Black or African American
 - Native Hawaiian or other Pacific Islander
 - White
 - Unknown

13.4 Registration Procedures

- a. All site staff (SWOG and CTSU Sites) will use OPEN to enroll patients to this study. OPEN is integrated with the CTSU Enterprise System for regulatory and roster data and, at the time of patient registration, initializes the patient in the Rave database. OPEN can be accessed at <https://open.ctsu.org> or from the OPEN tab on the CTSU members' side of the website at <https://www.ctsu.org>, or from the OPEN Patient Registration link on the SWOG CRA Workbench.
- b. Prior to accessing OPEN site staff should verify the following:
 - All eligibility criteria have been met within the protocol stated timeframes and the affirmation of eligibility on the Registration Worksheet has been signed by the registering investigator or another investigator designate. Site staff should refer to [Section 5.0](#) to verify eligibility.
 - All patients have signed an appropriate consent form and HIPAA authorization form (if applicable).

c. Access requirements for OPEN:

- Site staff will need to be registered with CTEP and have a valid and active CTEP-IAM account. This is the same account (user ID and password) used for the CTSU members' web site. Additional information about obtaining a CTEP-IAM account can be found at http://ctep.cancer.gov/branches/pmb/associate_registration.htm. Questions should be directed to the CTEP Associate Registration Help Desk by e-mail at [contact].
- To perform registrations, the site user must have been assigned the 'Registrar' role on the SWOG or CTSU roster:
 1. If you are a SWOG member, to perform registrations on SWOG protocols you must have an equivalent 'Registrar' role on the SWOG roster. Role assignments are handled through SWOG.
 2. If you are not a SWOG member, to perform registrations on SWOG protocols you must have the role of Registrar on the CTSU roster. Site and/or Data Administrators can manage CTSU roster roles via the new Site Roles maintenance feature under RSS on the CTSU members' web site. This will allow them to assign staff the "Registrar" role.

Note: The OPEN system will provide the site with a printable confirmation of registration and treatment information. Please print this confirmation for your records.

d. Further instructional information is provided on the OPEN tab of the CTSU members' side of the CTSU website at <https://www.ctsu.org> or at <https://open.ctsu.org>. For any additional questions contact the CTSU Help Desk at [name] or [contact].

13.5 Exceptions to SWOG registration policies will not be permitted.

- a. Patients must meet all eligibility requirements.
- b. Institutions must be identified as approved for registration.
- c. Registrations may not be cancelled.
- d. Late registrations (after initiation of treatment) will not be accepted.

14.0 DATA SUBMISSION SCHEDULE

14.1 Data Submission Requirement

Data must be submitted according to the protocol requirements for **ALL** patients registered, whether or not assigned treatment is administered, including patients deemed to be ineligible. Patients for whom documentation is inadequate to determine eligibility will generally be deemed ineligible.

14.2 Master Forms

Master forms can be found on the protocol abstract page on the SWOG website (www.swog.org) and (with the exception of the sample consent form and the Registration Worksheet) must be submitted on-line via the Web; see Section [14.3a](#) for details.

14.3 Data Submission Procedures

- a. Data collection for this study will be done exclusively through the Medidata Rave® clinical data management system. Access to the trial in Rave is granted through the iMedidata application to all persons with the appropriate roles assigned in Regulatory Support System (RSS). To access Rave via iMedidata, you must have an active CTEP-IAM account (check at <https://eapps-ctep.nci.nih.gov/iam/index.jsp>) and the appropriate Rave role (Rave CRA, Read-Only, Site Investigator) on either the LPO or participating organization roster at the enrolling site.

Upon initial site registration approval for the study in RSS, all persons with Rave roles assigned on the appropriate roster will be sent a study invitation e-mail from iMedidata. To accept the invitation, site users must log into the Select Login (<https://login.imedidata.com/selectlogin>) using their CTEP-IAM user name and password, and click on the “accept” link in the upper right-corner of the iMedidata page. Please note, site users will not be able to access the study in Rave until all required Medidata and study specific trainings are completed. Trainings will be in the form of electronic learnings (eLearnings), and can be accessed by clicking on the link in the upper right pane of the iMedidata screen.

Users that have not previously activated their iMedidata/Rave account at the time of initial registration approval for the study in RSS will also receive a separate invitation from iMedidata to activate their account. Account activation instructions are located on the CTSU website, Rave tab under the Rave resource materials (Medidata Account Activation and Study Invitation Acceptance). Additional information on iMedidata/Rave is available on the CTSU members' website under the Rave tab at www.ctsu.org/RAVE/ or by contacting the CTSU help Desk at [name] or by e-mail at [contact]

- b. You may also access Rave® via the SWOG CRA Workbench. Go to the SWOG web site (<http://swog.org>) and logon to the Members Area using your SWOG Roster ID Number and password. After you have logged on, click on *Workbenches*, then *CRA Workbench* to access the home page for the CRA Workbench and follow the link to Rave® provided in the left-hand navigation panel.

To access the CRA Workbench the following must be done (in order):

1. You are entered into the SWOG Roster and issued a SWOG Roster ID Number,

2. You are associated as an investigator or CRA/RN at the institution where the patient is being treated or followed,
3. Your Web User Administrator has added you as a web user and has given you the appropriate system permissions to view data for that institution.

For assistance with points 1 and 2 call the Operations Office at [name]. For point 3, contact your local Web User Administrator (refer to the "Who is my Web User Administrator?" function on the swog.org Members logon page).

For difficulties with the CRA Workbench, please email [contact].

- c. Institutions participating through the Cancer Trials Support Unit (CTSU) please refer to the CTSU Participation Table.

